9. SAFETY AND TOLERABILITY

Appendix A provides a list of data displays. Sample data displays are included in a separate document.

9.1. General Considerations

The analyses in this section will be provided for the safety population in the PC period, the extension evaluable population in the extension period, and for participants who took only povorcitinib 45 or 75 mg during the overall period, unless otherwise specified. Summary tables may be replaced with listings when appropriate; for instance, an AE frequency table may be replaced with a listing if it only contains a few unique preferred terms reported on relatively few participants.

9.2. Adverse Events

9.2.1. Adverse Event Definitions

A TEAE is any AE either reported for the first time or worsening of a pre-existing event after the first dose of study drug and up to 30 days after the last dose of study drug. Analysis of AEs will be limited to TEAEs, but data listings will include all AEs regardless of their timing in relation to study drug administration. For purposes of analysis, all AEs will be considered TEAEs unless the AE can unequivocally be defined as not treatment-emergent.

A TEAE in the PC period is any AE with a start time after the first dose of study drug in the PC period and until the end of the safety follow-up, or prior to the first dose in the extension period for participants who entered in to the extension period.

A TEAE in the extension period is any AE with a start time after the first dose of study drug in the extension period and until the end of the safety follow-up.

For participants who took only povorcitinib 45 or 75 mg during overall period, a TEAE is any AE with a start time after the first dose of study drug in the PC period and until the end of the safety follow-up.

Adverse events will be tabulated by MedDRA PT and SOC. Severity of AEs will be graded using the National Cancer Institute CTCAE v5.0. The CTCAE reporting guidelines and grading details are available on the Cancer Therapy Evaluation Program website.

The subset of AEs considered by the investigator to be related to study drug will be considered to be treatment-related AEs. If the investigator does not specify the relationship of the AE to study drug, the AE will be considered to be treatment-related. The incidence of AEs and treatment-related AEs will be tabulated. In addition, serious TEAEs will also be tabulated.

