8.9. Follow-Up

The safety follow-up period is the interval between the EOT visit and the scheduled follow-up visit (EOS), which should occur approximately 30 days after the EOT visit (or after the last dose of study drug if the EOT visit was not performed). Adverse events and SAEs must be reported up until 1) at least 30 days after the last dose of study drug or 2) until toxicities resolve, return to baseline, or are deemed irreversible, whichever is longer. Reasonable efforts should be made to have the participant return for the follow-up visit and report any AEs that may occur during this period. In exceptional cases when the participant cannot return to the site for the safety follow-up visit, the participant should be contacted by telephone/video call for assessment of AEs and SAEs and the site should properly document the contact.

9. ADVERSE EVENTS: DEFINITIONS AND PROCEDURES FOR RECORDING, EVALUATING, FOLLOW-UP, AND REPORTING

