9.3. Recording and Follow-Up of Adverse Events and/or Serious Adverse Events

Adverse Event and Serious Adverse Event Recording

- An AE/SAE that begins or worsens after informed consent is signed should be recorded on the Adverse Event Form in the eCRF. AEs/SAEs should be reported for randomized participants, but only SAEs need to be reported for screen failure participants. For randomized participants, conditions that were present at the time informed consent was given should be recorded on the Medical History Form in the eCRF. For detailed information, refer to the eCRF guidelines.
- When an AE/SAE occurs, it is the responsibility of the investigator to review all documentation (eg, hospital progress notes, laboratory reports, and diagnostic reports) related to the event.
- The investigator (or delegate) will then record all relevant AE/SAE information in the eCRF.
- It is **not** acceptable for the investigator to send photocopies of the participant's medical records in lieu of completing the Adverse Event Form in the eCRF.
- There may be rare instances when copies of medical records for certain cases are requested. In this case, all participant identifiers, with the exception of the participant number, will be redacted by the site staff on the copies of the medical records before submission. These records can be submitted to Incyte Pharmacovigilance by email/fax per the contact information listed in the Study Reference Manual or as per SAE completing guidelines.
- The investigator will attempt to establish a diagnosis of the event based on signs, symptoms, and/or other clinical information. Whenever possible, the diagnosis (not the individual signs/symptoms) will be documented as the AE/SAE. When a clear diagnosis cannot be identified, each sign or symptom should be reported as a separate AE/SAE.

To the extent possible, each AE/SAE should be evaluated to determine the following:

- The severity grade (CTCAE v5.0 Grade 1 to 5). See below for further instructions on the assessment of intensity.
- Whether there is at least a reasonable possibility that the AE is related to the study drug: suspected (yes) or not suspected (no). See below for further instructions on the assessment of causality.
- The start and end dates, unless unresolved at the final safety follow-up visit.
- The action taken with regard to study drug as a result of the AE/SAE(s).

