- There may be situations in which an SAE has occurred and the investigator has minimal information to include in the initial report. However, the causality assessment is one of the criteria used when determining regulatory reporting requirements. Therefore, it is very important that the investigator always make an assessment of causality based on the available information for every event before the initial transmission of the SAE.

- The investigator may change his/her opinion of causality in light of follow-up information and submit the updated causality assessment.

Follow-Up of Adverse Events and Serious Adverse Events

- The investigator is obligated to perform or arrange for the conduct of supplemental measurements and/or evaluations as medically indicated or as requested by the sponsor to elucidate the nature and/or causality of the AE or SAE as fully as possible. This may include additional laboratory tests or investigations, histopathological examinations, or consultation with other health care professionals.
- Once an AE is detected, it should be followed in the AE eCRFs until it has resolved or until it is judged to be permanent; assessment should be made at each visit (or more frequently if necessary) of any changes in severity, the suspected relationship to the study drug, the interventions required to treat the event, and the outcome.
- When the severity of an AE changes over time for a reporting period (eg, between visits), each change in severity will be reported as a separate AE.
- If a participant dies during participation in the study or during a recognized follow-up period, the investigator will provide the sponsor with a copy of any postmortem findings, including histopathology.
- Updated SAE information will be recorded in the originally completed eCRF and reported to Incyte Pharmacovigilance (via the AE and SAE eCRFs in the EDC) until resolution, stabilization, the event is otherwise explained, or the participant is lost to follow-up.
- Any updated SAE data (including SAEs being downgraded to nonserious) will be submitted to the sponsor (or designee) within 24 hours of receipt of the information.

See Appendix E for the management of PHL cases.

9.4. **Reporting of Serious Adverse Events**

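### The SAP assigns extension-period TEAEs by start time alone, so an AE record opened only because an event improved can count as a new extension event

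*SAP*

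**What the plan says.** SAP 9.2.1 opens with a general rule that Protocol 10.4.3 shares: "A TEAE is any AE either reported for the first time or worsening of a pre-existing event after the first dose of study drug", limited to 30 days after the last dose. The section then adds three period rules, which Protocol 10.4.3 does not have.

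- **PC period:** "A TEAE in the PC period is any AE with a start time after the first dose of study drug in the PC period". It runs to the end of safety follow-up or, for those who continue, to the first extension dose.
- **Extension:** "A TEAE in the extension period is any AE with a start time after the first dose of study drug in the extension period". It runs to the end of safety follow-up.
- **Overall period** (participants who took only 45 mg or only 75 mg): the same start-time form, counted from the first PC dose to the end of safety follow-up.

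None of the three compares severity with an earlier grade or says how several records of one event are joined. In case of doubt, "all AEs will be considered TEAEs unless the AE can unequivocally be defined as not treatment-emergent".

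On recording, Protocol 9.3 says that when severity changes over a reporting period, "each change in severity will be reported as a separate AE". Improvement is not exempted. The same section lists what is determined for each AE, including "The start and end dates, unless unresolved at the final safety follow-up visit".

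Extension AEs are tabulated by treatment sequence within the Week 16 responder and nonresponder cohorts (SAP 5.2 and 9.2.2). The safety follow-up visit is 28 (+7) days after the last dose in Protocol Table 4 and Section 7.2, but "approximately 30 days after the EOT visit" in Protocol 8.9.

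**The concern.** The recording rule and the counting rule are each workable alone, but together they let improvement count as a new event. The recording rule splits one event into several dated records, and the counting rule looks only at the date. SAP 4.1.3 resets the safety baseline for measurements at the first extension dose, but the AE rule has no matching reference grade.

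The extension tables should show what emerged under the extension dose. Under the literal rule they would also hold the tail of events that began on the previous treatment, including placebo. For the PC and overall periods, two definitions in one section can give different answers for the same record, and a programmer must choose between them. The same is true of the end of the counting window.

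**Working it through.** The plan states no figure to reproduce, so the check applies the rules to example records and then sizes one misclassification.

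**1. Rule trace.** The days are illustrative. Sixteen weeks is 16 × 7 = 112 days, so the first extension dose is placed on Day 113. Each re-graded record is dated at its grade change. The comparison rule counts a record only if the event is new in the period or its grade is above the grade at the start of the period.

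| Event history | Period | Literal SAP rule | New-or-worse rule |
|---|---|---|---|
| Grade 2 Day 100, Grade 1 Day 120 | Extension | 1 | 0 |
| Grade 3 Day 100, Grade 2 Day 120, Grade 1 Day 130 | Extension | 2 | 0 |
| Grade 1 Day 100, Grade 2 Day 120 | Extension | 1 | 1 |
| New Grade 1 Day 120 | Extension | 1 | 1 |
| Grade 2 Day -5, Grade 1 Day 10 | PC | 1 | 0 |

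The rules agree on new and worsening events and differ only on improving ones.

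**2. Does the general definition repair this?** It is anchored to the first dose of study drug. In the first two rows the event was first reported after that dose, so it already qualifies as a TEAE, and the extension rule then places its later record by date. The general definition does not exclude that record. In the last row the event is neither first reported nor worse after the first dose, so the general rule excludes it while the PC rule includes it.

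**3. Window.** The general rule ends at "worsening of a pre-existing event after the first dose of study drug and up to 30 days after the last dose of study drug". The period rules end with safety follow-up. With the visit at Day 28 to 35 after the last dose, the end point differs from 30 days by 28 − 30 = −2 to 35 − 30 = +5 days. An event starting on Day 33 before a Day 35 visit is a TEAE under the period rule and not under the general rule.

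**4. Size of one case.** Tables count participants, so one affected participant with no other TEAE in the row adds 1/n.

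- Four arms by two cohorts gives 8 subgroups. If all 140 enter and split evenly, 140 / 8 = 17.5, and 1 / 17.5 = 5.7 points.
- If 10% do not enter (an assumption), 126 / 8 = 15.75, and 1 / 15.75 = 6.3 points.
- If placebo nonresponders follow the 15% planning rate, 35 × 0.85 = 29.75, about 30, and 1 / 29.75 = 3.4 points.

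**5. Range for more than one case.** The documents give no frequency, so this is assumption only. Let t be the true proportion with an extension TEAE and q the proportion of the remaining participants whose only record is an improving carry-over. The reported proportion is t + (1 − t)q.

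- t = 30%: q = 2% gives 31.4%, and q = 20% gives 44.0%.
- t = 50%: q = 2% gives 51.0%, and q = 20% gives 60.0%.

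**The case against.** **The period sentences may only allocate TEAEs to periods, not redefine them.** On that reading a screening AE that improves after Day 1 is not treatment-emergent. A reader might infer that such events will certainly enter the PC tables. The documents do not support that, because the general definition arguably keeps them out. What stands for the PC and overall periods is a conflict of wording. The reading does not help the extension, for the reason in step 2 of the working.

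**The start date of a re-graded record is inferred.** Protocol 9.3 frames the splitting rule by reporting period, such as between visits, and refers to eCRF guidelines for detail. No passage states which start date the new record takes. This objection stands. The finding is conditional on the record being dated at the grade change, which follows naturally from a separate AE with its own dates.

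**The reach is limited.** This also stands. Participants already counted in a row add nothing. Sequence labels keep prior placebo exposure visible. An improving record enters a Grade 3 or higher table only on a fall from Grade 4 to Grade 3. Treatment-related status is the investigator's judgement, so assignment to the extension does not by itself put a record in those tables. Protocol 9.4 treats recurrence, complication or progression of an SAE as follow-up to the original event, so the serious-event tables may be less affected.

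**The point sizes are only 1/n.** They are not estimates of bias. A reader might go to the smallest cell, placebo responders at 35 × 0.15 = 5.25, and quote 1 / 5.25 = 19 points as the effect or 5.25 as a ceiling. Neither is supported: 15% is a planning assumption for itch response, and the rule that defines a Week 16 responder is not visible.

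**AEs must be reported for at least 30 days after the last dose (Protocol 8.4.1 and 8.9).** A reader might infer from the visit schedule that collection can stop at 28 days. It cannot, because 28 days is visit timing and not the minimum reporting period. What remains is that the SAP names two different end points for counting.

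**Conclusion.** The concern holds in a limited form. Followed literally, SAP 9.2.1 counts as an extension TEAE an event that began in the PC period and only improved after the first extension dose, provided the re-graded record is dated at the grade change. The general definition does not prevent this, and the default for doubtful cases favours counting. For the PC and overall periods, the section contradicts itself on the new-or-worsening test. In all three periods the stated end of the window differs from 30 days after the last dose.

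The effect is confined to descriptive safety tables. No efficacy result or formal comparison is touched. Its frequency is unknown, and each affected participant moves a row by 1/n: about 3.4 points in the illustrative placebo nonresponder subgroup, and 5.7 to 6.3 points under an even split. The documents do not support saying that the extension tables will be materially inflated. They do show a rule that can produce the error and is easily corrected.

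**What to change.** In SAP 9.2.1, replace the three start-time rules with one form:

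- A period TEAE is an AE with first onset in that period, or one whose CTCAE grade exceeds the last grade before that period's first dose.
- The window runs from that first dose to the earlier of the next period's first dose or 30 days after the last dose. For the overall period only the 30-day limit applies.
- A record opened only by a fall in grade of a continuing event (same preferred term, contiguous dates) is not counted.

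The linking rule should be written in advance and applied by program. A later blinded case review cannot be relied on: investigators know the extension dose (Protocol 4.1), and the sponsor is unblinded at the primary analysis, once the PC period is complete (SAP 3).

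The cost is an SAP wording change and a small programming step, with no new data. The downside is that a genuine new episode adjoining an earlier one of the same preferred term could be linked to it and missed. The AE listings, which include all AEs whatever their timing, would show such cases.

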9.2.2. Adverse Event Summaries

Adverse events will be summarized by treatment group and povorcitinib dose groups combined for the safety population in the PC period, and by treatment group and overall in each cohort (ie, Week 16 responders and nonresponders) for the extension evaluable population in the extension period, and by treatment group and overall for participants who took only povorcitinib 45 or 75 mg during the overall period.

An overall summary of AEs will include the following:

- Number (%) of participants reporting any TEAEs
- Number (%) of participants reporting any serious TEAEs
- Number (%) of participants reporting any Grade 3 or higher TEAEs
- Number (%) of participants reporting any treatment-related TEAEs
- Number (%) of participants who temporarily interrupted study treatment because of TEAEs
- Number (%) of participants who permanently discontinued study treatment because of TEAEs
- Number (%) of participants who had a fatal TEAE
- Number (%) of participants who had TEAE requiring concomitant medication

The following summaries will be produced by MedDRA term (if 10 or fewer participants appear in a table, a listing may be appropriate):

- Summary of TEAEs by MedDRA SOC and PT
- Summary of TEAEs by MedDRA PT in decreasing order of frequency
- Summary of TEAEs by MedDRA SOC, PT, and maximum severity
- Summary of TEAEs by MedDRA SOC, PT, and CTCAE grade category
- Summary of Grade 3 or higher TEAEs by MedDRA SOC and PT
- Summary of Grade 3 or higher TEAEs by MedDRA PT in decreasing order of frequency
- Summary of serious TEAEs by MedDRA SOC and PT
- Summary of serious TEAEs by MedDRA PT in decreasing order of frequency
- Summary of treatment-related TEAEs by MedDRA SOC and PT
- Summary of treatment-related TEAEs by MedDRA PT in decreasing order of frequency
- Summary of Grade 3 or higher treatment-related TEAEs by MedDRA SOC and PT
- Summary of treatment-related serious TEAEs by MedDRA SOC and PT
- Summary of TEAEs with a fatal outcome by MedDRA SOC and PT
- Summary of TEAEs leading to dose interruption by MedDRA SOC and PT
- Summary of TEAEs leading to discontinuation of study drug by MedDRA SOC and PT
- Summary of TEAEs requiring concomitant medications by MedDRA SOC and PT

9.3. Clinical Laboratory Tests

9.3.1. Laboratory Value Definitions

Laboratory values, change from baseline values, and percent change from baseline values will be summarized descriptively by visit, and non-numeric test values will be tabulated when necessary. Baseline will be determined according to Section 4.1.3. The last record before administration in the highest priority will be considered the baseline record. For baseline laboratory candidates with the same date and time in the same priority category, additional rules may be provided after consultation with the medical monitor to delineate which value will be defined as baseline.

9.3.2. Laboratory Value Summaries

All test results and associated normal ranges from central laboratories will be reported in SI units. All tests with numeric values will have a unique unit per test. Any laboratory test results and associated normal ranges from local laboratories will be converted to SI units.

When there are multiple nonmissing laboratory values for a participant's particular test at a scheduled visit, laboratory values have higher priority over local laboratory values. If a tie still exists, the laboratory value with the smallest laboratory sequence number will be used in by-visit summaries. In addition, boxplots will be provided for creatine kinase, hemoglobin, hematocrit, platelet count, high sensitivity C-reactive protein, lymphocyte absolute count, neutrophil absolute count, white blood cell count, total cholesterol, HDL, LDL, and HDL/LDL ratio.

For test results that will be summarized with available normal ranges, the number and percentage of participants with the laboratory values being low (but never high), normal, high (but never low), and both low and high will be calculated for each test. This shift summary will be produced for each test. The denominator for the percentage calculation will use the number of participants in the baseline category (ie, low, high, normal, missing) as the denominator for the percentage in each of the categories during the study.

Severity grades will be assigned to laboratory test values based on the numerical component of CTCAE v5. Shift tables will also be presented showing change in CTCAE grade from baseline to the worst grade postbaseline. Separate summaries for abnormally high and abnormally low laboratory values will be provided when the laboratory parameter has both high and low grading criteria. The denominator for the percentage calculation will be the number of participants in the baseline category. The number of participants who experienced worsening of laboratory abnormalities will be summarized by maximum severity.

9.3.3. Potentially Clinically Important Laboratory Values

Criteria for potentially clinically important laboratory values are listed in Table 6. The number and percentage of participants with postbaseline laboratory values that meet each criterion will be summarized at each scheduled visit by treatment group. Participants with potentially clinically important laboratory values will also be listed.

Laboratory Parameter	Grade (Criteria)
Hemoglobin	Grade 2 (80 to < 100 g/L) Grade 3 (< 80 g/L)
Lymphocytes	Grade 2 (0.5 to $< 0.8 \times 10^{9}/L$) Grade 3 (0.2 to $< 0.5 \times 10^{9}/L$) Grade 4 ($< 0.2 \times 10^{9}/L$)
Neutrophils	Grade 2 (1.0 to $< 1.5 \times 10^{9}/L$) Grade 3 (0.5 to $< 1.0 \times 10^{9}/L$) Grade 4 ($< 0.5 \times 10^{9}/L$)

 Table 6:
 Criteria for Potentially Clinically Important Laboratory Values

Laboratory Parameter	Grade (Criteria)
Platelets	Grade 2 (50 to $< 75 \times 10^{9}/L$) Grade 3 (25 to $< 50 \times 10^{9}/L$)
	Grade 4 ($< 25 \times 10^{9}/L$)
Creatinine	Grade 2 (> 1.5 to 3 × ULN or > 1.5 to 3 × baseline) Grade 3 (> 3 to 6 × ULN or > 3 × baseline) Grade 4 (> 6 × ULN)
Creatine kinase	Grade 2 (> 2.5 to 5 × ULN) Grade 3 (> 5 to 10 × ULN) Grade 4 (> 10 × ULN)

Table 6: Criteria for Potentially Clinically Important Laboratory Values (Continued)

9.3.4. Potential Drug-Induced Liver Injury Events

According to FDA's guidance on Drug-Induced Liver Injury (2009), the criteria for potential DILI events include the following:

- ALT \geq 3 × ULN
- ALT \geq 5 × ULN
- ALT $\geq 10 \times ULN$
- ALT $\geq 20 \times ULN$
- AST \geq 3 × ULN
- AST \geq 5 × ULN
- AST $\geq 10 \times ULN$
- AST $\geq 20 \times ULN$
- ALT or AST \geq 3 × ULN
- ALT or AST \geq 5 × ULN
- ALT or AST $\geq 10 \times ULN$
- ALT or AST $\geq 20 \times ULN$
- Alkaline phosphatase $\geq 1.5 \times ULN$
- Total bilirubin $\geq 2 \times ULN$
- ALT and/or AST \ge 3 × ULN and total bilirubin \ge 2 × ULN

Note that combination of values need to be measured on the same day.

The number and percentage of participants with postbaseline liver specific function test values that meet these criteria will be presented at each scheduled visit by treatment group. Participants with potential DILI events will also be listed.

